3.3 Subject selection

3.3.1 General characteristics of the proposed subject populations(s)

Participants who participated in the core study (IDE G100298, University of Pittsburgh PRO10080021) may be eligible for the extension study if they have had positive clinical and research outcomes after 6 months of implantation and meet the eligibility criteria described in Sections 3.3.3 and 3.3.4.

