3.3.3 Inclusion criteria

- 1) Participant in PRO10080021 study (IDE G100298) who is at least 6 months post-implant
- 2) Have no unresolved significant adverse events during participation in PRO10080021
- 3) Have demonstrated at least 4-dimensional control of a virtual or real robotic arm during participation in PRO10080021
- 4) Have a stable psychosocial support and caregivers who are able to perform the necessary daily care of the participant's skin and pedestal site; This requires that the subject identify a caregiver and a back up who have been in place for greater than 6 months and are able to provide needed physical and psychosocial support. This will be assessed by the study PI and neurosurgeon.
- 5) Age 18-70 years old at the time of consent and planned explant
- 6) Have a life expectancy greater than 12 months as assessed by the study principal investigator and neurosurgeon sub-investigator
- 7) Live within 1 hour of the University of Pittsburgh, or be willing to travel there, once per week for BMI testing
- 8) Interested in having the NeuroPort arrays remain in place for 6 months to 4 years beyond the 1 year implantation that is part of PRO10080021. Participants can

decide to extend the implantation for any duration between 6 months and 4 years. This can be decided at any point during the study.

- 9) Participation is not expected to have an adverse effect on mental well-being as judged by the rehabilitation psychologist
- 10) Documentation of informed consent is obtained from the participant or their legal representative

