3.5 Study outcome evaluations

3.5.1 Study endpoints

The NeuroPort Arrays will be removed up to 5 years after implantation. A participant will be considered a success for safety if the device is not explanted for safety reasons during the 5 year post-implant evaluation. If the subject experiences treatment resistant (serious) adverse events, he or she will be withdrawn and the arrays will be explanted early (See Section E 3.4.4). The study may also end early if the subject is non-compliant (See Section E 3.4.4).

If the participant wishes to leave the NeuroPort Array implanted after 5 years, the participant will be counseled that they should have the NeuroPort Array removed and that not doing so could result in clinically significant adverse events. They will also be informed that brain-machine interface training will not continue. The consent form includes a statement that participants will be financially liable for any medical care resulting from complications of not having the device removed upon instruction of the study PI. We will however allow participants to have the device removed at anytime and the explantation costs would be covered by this study.

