Specific Aim 3: Source localization (combining the MEG and structural MRI data) will be used to identify the anatomical foci of cortical activation controlling imagined and/or attempted movement. The coordinates (x,y,z) of the center of activation can be computed with fMRI or MEG relative to the head coordinate system defined using bony landmarks. The location and area of cortical activation measured by fMRI and MEG during imagined and/or attempted movement will be compared for each subject. A paired t-test will be used to compare location and area of cortical activation measured by the two imaging techniques using data from all participants, although the power of this test may be limited by sample size. Qualitative comparisons will be informative and we expect agreement between the two imaging techniques in terms of localizing the area for array implantation. MEG potentially offers additional information due to higher temporal resolution.

Specific Aim 3a: Cortical modulation will be calculated as the power of the 4-40 Hz frequency band of MEG data that is recorded during imagined and/or attempted movement. Specific Aim 3a will be evaluated by applying repeated measures ANOVA to test for differences in modulation (magnitude and total area) during imagined and/or attempted movement during the pre-surgical procedures and the follow-up sessions.

Specific Aim 4: Sleep quality measures will be correlated to BMI performance on the following day while controlling for differences in task difficulty. Linear regression will be used to determine the most predictive sleep quality metrics.

The study will be considered a success if the device is not explanted for safety reasons during the 12-month to 5 year post-implant evaluation. This study is not being proposed to support marketing applications (510(k) or PMA) for the NeuroPort Arrays. Instead, the goal is to demonstrate that three-dimensional microelectrode arrays provide a safe way to record sufficient neural information for controlling complex assistive devices that will increase the independence of individuals with disabilities.

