The primary risks of chronic recording center around the long-term presence of the NeuroPort Arrays and Patient Pedestals. The risks associated with the chronic implantation of the NeuroPort Arrays are expected to be similar to those observed with the implantation of other chronic devices such as deep brain stimulators and cochlear implants. Some of these include, but are not limited to thrombosis, embolism, body rejection phenomena, neurological complications, and infection (meningitis and cellulitis) (see full list below). The most common complication for these types of devices is infection. Infection rates for other implanted devices requiring a craniotomy range from 4 to 12% [20-22]. The outcome of infection may be serious and may lead to brain edema or other sequelae. If the infection cannot be treated with antibiotics, the NeuroPort Arrays may need to be explanted. Some of these procedures included in the infection risk estimate are more invasive than that proposed in the current study. Because we will perform a smaller craniotomy with a wound closure away from the implantation site, and due to the lack of clinical adverse events observed in the BrainGate trial, we believe that the risk of infection for a single NeuroPort Array is at the low end of this range (approximately 5-6%). Based on our team's experience with other neurosurgical procedures, we estimate the elevated risk of infection due to the presence of two percutaneous Patient Pedestals to be less than 50% of the current risk. Therefore the expected risk of infection for the proposed study is approximated to be less than 9%. Most of the risk for infection is due to environmental factors in the operating room and therefore having two percutaneous sites only introduces an incremental increase in the risk of infection.

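### The extension's 5-year safety success is counted from implant in participants selected 6 to 13 months later, and sections 3.5.1 and 3.5.3 give different windows for it

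*Combined protocol and SAP*

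**What the plan says.** The extension protocol states its safety endpoint twice.

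- Section 3.5.1, for the participant: success if the device is "not explanted for safety reasons during the 5 year post-implant evaluation".
- Section 3.5.3, for the study: success if the device is "not explanted for safety reasons during the 12-month to 5 year post-implant evaluation".

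The population comes from other sections. Section 3.5.2 limits the extension to the core study's participants, of whom at most 5 are implanted. Under section 3.3.1 they "may be eligible for the extension study if they have had positive clinical and research outcomes after 6 months of implantation". Section 3.3.3 requires a participant "who is at least 6 months post-implant" and adds a safety criterion, "Have no unresolved significant adverse events during participation in PRO10080021", and a performance criterion, "Have demonstrated at least 4-dimensional control of a virtual or real robotic arm during participation in PRO10080021". Section 3.4.2 places consent and screening between 6 and 13 months after implant.

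The core protocol has its own safety endpoint (sections 2.5.1 and 2.5.3): no explant for safety reasons in the 12 months after implant.

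Section 3.5 gives no denominator for the 5-year result and does not say that the result is conditional on having entered the extension.

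**The concern.** The entry criteria overlap the endpoint. To be scored under section 3.5.1 a participant must already have gone 6 to 13 months without a safety explant, and those months are then credited toward a 5-year post-implant success. Someone explanted for safety before entry, or kept out by an unresolved significant adverse event, is never scored on this endpoint.

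Section 3.5.2 describes this as the first evaluation of long-term implantation in this population, and section 3.5.3 states the aim as showing that the arrays are a safe means of recording. A 5-year post-implant success is easily read as describing everyone implanted, when the rule as written describes selected survivors. The signal-quality and performance trends for years 1 to 5 have the same limit, because they come only from people who showed good control and good outcomes early.

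The second problem is the mismatch between the two windows. The same event can be a failure under one section and outside the window of the other.

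**Working it through.** The plan gives no sample-size, power or rate figure for this endpoint, so there is nothing to reproduce. The check sets the rules side by side and then illustrates the effect on a count.

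**1. Guaranteed time under section 3.5.1.** Five years is 60 months. Entry at month 6 gives 6/60 = 10% of the clock free of safety explant by construction. Entry at month 13 gives 13/60 = 22%. Under the section 3.5.3 window the guaranteed time is at most 13 − 12 = 1 month, and only for those who enter after month 12.

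**2. How each rule scores a safety explant.**

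| Safety explant | Core 12-month endpoint (2.5.1, 2.5.3) | Section 3.5.1 | Section 3.5.3 |
|---|---|---|---|
| Month 4 (before extension entry is possible) | Failure | Not scored | Not scored |
| Month 9, after extension consent | Failure | Failure | Before the window opens |
| Month 30, in the extension | Success | Failure | Failure |

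The first row shows the selection: the event is counted once, in the core result, and is absent from the 5-year result. The second row shows the conflict between sections 3.5.1 and 3.5.3.

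**3. Effect on a count (illustration).** Assume 5 implanted, every participant without an early safety explant entering the extension, and no later safety explant. Intervals are exact (Clopper-Pearson) 95%.

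| Early safety explants | Extension participants only | All implanted |
|---|---|---|
| 0 | 5/5 = 100% (47.8% to 100%) | 5/5 = 100% (47.8% to 100%) |
| 1 | 4/4 = 100% (39.8% to 100%) | 4/5 = 80% (28.4% to 99.5%) |
| 2 | 3/3 = 100% (29.2% to 100%) | 3/5 = 60% (14.7% to 94.7%) |

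**4. General form.** Let p_e be the chance of a safety explant before entry and p_l the chance after it, with p_l taken to be the same whoever enters. Success among those who enter is 1 − p_l. Success from implant in all implanted is (1 − p_e)(1 − p_l). The gap is p_e(1 − p_l). The documents give neither value. With both assumed to be 5%, the figures are 95.0% and 0.95 × 0.95 = 90.3%. With both assumed to be 20%, they are 80.0% and 0.80 × 0.80 = 64.0%.

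**5. Chance that it matters.** The chance of at least one early safety explant among 5 is 1 − (1 − p_e)^5. That is 1 − 0.98^5 = 10% if p_e is 2%, and 1 − 0.80^5 = 67% if p_e is 20%. The range is wide because the rate is unknown.

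**The case against.** The strongest reply is that no failure is lost. The core protocol scores every implanted participant over the first 12 months, so safety explants at month 4 and at month 9 are both core failures. The same DSMB oversees both studies (section 3.5.4). A reader might infer that early failures drop out of the programme's safety record. The documents do not support that: those failures are missing only from the 5-year result.

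Nor does the plan promise a percentage. Section 3.5.1 classifies one participant, section 3.5.3 is a yes-or-no statement about the study, and section 2.5.2 specifies single-subject analyses. The denominators above are inferred from the endpoint's place in the extension protocol. It would be wrong to say that the plan will report 100%.

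Two further inferences should be resisted.

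- **Infection risk as the size of the problem.** Section 4.1 puts infection risk with two pedestals below 9%, and 1 − 0.91^5 = 38% would then bound the chance of any infection among five people. But infection is not safety explant. Section 3.4.4 lists treatment-resistant infection as possible grounds for removal, and a treated, resolved infection neither fails the endpoint nor bars entry.
- **Most of the hazard falling before entry.** Section 4.1 says "Most of the risk for infection is due to environmental factors in the operating room", which describes the source of infection and gives no time course. The same section says that infection risk continues after surgical healing because the pedestal passes through the skin.

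Finally, an extension can enrol only people who are still implanted, and its criteria are openly stated. That is a fair defence of the eligibility rules, which need not change. It does not justify counting the 5 years from implant without a condition attached, and it does not resolve the two windows.

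**Conclusion.** The point holds as one of endpoint definition and interpretation. Applied as written, section 3.5.1 credits selected survivors with a 5-year post-implant safety success that includes 6 to 13 months in which they could not have failed. Section 3.5.3 contradicts it on the window.

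The size can be illustrated but not estimated. With 5 implanted, one early safety explant and the other four entering and completing, the counts are 4/4 and 4/5. That rests on the assumed scenario and on reading the extension endpoint as applying to extension participants only. With no early safety explant the two counts agree. The intervals overlap heavily at this sample size, so power is not the issue.

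The change is worth making because the 5-year statement will be read as a long-term safety result, and because the two sections cannot both be followed for a safety explant that occurs after extension consent and before month 12.

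**What to change.** - Use one extension window in sections 3.5.1 and 3.5.3. Twelve months to 5 years is a workable choice because it adjoins the core 0 to 12 month endpoint. A clock starting at consent is less tidy: each participant would have a different origin, and for anyone consenting before month 12 it would overlap the core window.
- State in both sections that the extension safety result, and the signal and performance trends for years 1 to 5, are conditional on extension entry.
- Give any 5-year post-implant safety statement from the implant date, as x of all participants implanted under PRO10080021. List each person's implant duration, status at last contact and reason for explant. Duration belongs in the list because section 3.3.3 lets participants choose an extension of 6 months to 4 years, so not all will have 5 years of exposure.

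Eligibility and data collection stay as they are. The cost is a few sentences and one listing built from data already collected. The downside is that the 5-year figure may look less favourable.

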3.5.2 Sample size determination

This is the first study to evaluate a long-term implantation of microelectrode arrays in individuals with spinal cord injury (or other impairment resulting in upper limb paralysis). Because this is a feasibility study, we feel that it is appropriate to begin with a small sample size in this initial investigation. We are recruiting up to 5 participants for PRO10080021 and only these people would be eligible for the current study.

3.5.3 Outcome data and data analysis

Specific Aim 1a will be fulfilled through monthly clinical examinations as well as observations made by the research staff, participant, or their caregiver throughout the trial. Research staff will document volunteered and observed adverse events at least weekly during the BMI training sessions. Adverse events will be documented and reported to University of Pittsburgh IRB and to the FDA in accordance with the respective reporting requirements and in the annual report. This documentation will serve as documentation of the safety of device in this small sample.

Specific Aim 1b is to characterize signal quality (firing rate, number of units recorded) over the duration of implantation. Data to support this aim will be collected at least weekly during the BMI training sessions. Our primary method of analysis will be to plot the trends in signal quality measures over time. The trend will be quantified using regression techniques.

Specific Aim 2 is to demonstrate that individuals with tetraplegia can learn to successfully control of a variety of external devices and computer-driven tasks using signals recorded with the NeuroPort Array. In addition to video documentation of brain-controlled device operation, we will quantify the number of degrees of freedom achieved by each participant at regular intervals for the duration of implantation. Multiple baselines will be defined as the level of computer assist will decrease with training. We will use regression to quantify changes in performance at a given assist level. Similarly, trends in success rate and computer assist level for a given task will be quantified over the duration of the trial using regression.

Specific Aim 3: Source localization (combining the MEG and structural MRI data) will be used to identify the anatomical foci of cortical activation controlling imagined and/or attempted movement. The coordinates (x,y,z) of the center of activation can be computed with fMRI or MEG relative to the head coordinate system defined using bony landmarks. The location and area of cortical activation measured by fMRI and MEG during imagined and/or attempted movement will be compared for each subject. A paired t-test will be used to compare location and area of cortical activation measured by the two imaging techniques using data from all participants, although the power of this test may be limited by sample size. Qualitative comparisons will be informative and we expect agreement between the two imaging techniques in terms of localizing the area for array implantation. MEG potentially offers additional information due to higher temporal resolution.

Specific Aim 3a: Cortical modulation will be calculated as the power of the 4-40 Hz frequency band of MEG data that is recorded during imagined and/or attempted movement. Specific Aim 3a will be evaluated by applying repeated measures ANOVA to test for differences in modulation (magnitude and total area) during imagined and/or attempted movement during the pre-surgical procedures and the follow-up sessions.

Specific Aim 4: Sleep quality measures will be correlated to BMI performance on the following day while controlling for differences in task difficulty. Linear regression will be used to determine the most predictive sleep quality metrics.

The study will be considered a success if the device is not explanted for safety reasons during the 12-month to 5 year post-implant evaluation. This study is not being proposed to support marketing applications (510(k) or PMA) for the NeuroPort Arrays. Instead, the goal is to demonstrate that three-dimensional microelectrode arrays provide a safe way to record sufficient neural information for controlling complex assistive devices that will increase the independence of individuals with disabilities.

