This study will include a sleep diary and brain activity measured during sleep using EEG and/or intracortical recordings from the NeuroPort electrode arrays.

The aims remain the same for the proposed extension study, however we will have the opportunity to investigate these aims during the 1-5 year post-implant period. We also expect that we may see a decline in BMI performance over time as signal quality declines. This will be an opportunity to see if neuroplasticity, or novel training methods, can compensate for this degradation in performance.

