3.4.2 Experimental procedures

This study is an optional extension to PRO10080021. Consent and screening for this study may occur as early as 6 months after implant and up to 13 months after implant (the maximum duration allowed in the original protocol). BMI testing will occur as described in the original protocol with similar ongoing clinical monitoring and follow-up as described below:

Brain-Machine Interface (BMI) Training/Testing:

Neural recording will be conducted for the duration of implantation. The recorded neural data will be used to operate a BMI system that allows the participant to control a computer cursor, virtual object, or assistive device. While the NeuroPort Arrays are implanted, we will conduct BMI training for up to 8 hours per day for up to 5 days per week. At least 1 session per week will be attempted while the array is implanted. BMI testing may occur at the University of Pittsburgh, UPMC, or in the participant's home. Rest, meals, and other breaks will be scheduled as needed. We may not conduct training sessions every day. This will be determined by the research staff and the subject. Also, we may not conduct testing sessions for up to 8 weeks per year. Since participants will have already completed 1 year of testing, we hope to minimize the burden on participants while still collecting valuable data related to signal quality and BMI control. The subject will go no longer than 3 weeks between testing sessions. This will assure that the study team can continue to monitor the wound site and well being of the participant.

At the beginning of each BMI testing session, an investigator will connect the Patient Cable to the Patient Pedestal. We may also record neural activity using EEG electrodes which are placed on the scalp in order to measure larger networks of brain activation. There are two types of behavioral tasks that the subject will participate in as part of the BMI training/testing: 1. Open-loop and 2. Closed Loop. These tasks are the same as described in Section 2.4.2.

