Neural and behavioral data will be recorded during each BMI session in order to address the Specific Aims. As described in Section 2.4.2, we will track neural data, including the number of single units and the average firing rate over the duration of the implant. Behavioral data may include kinematics of a cursor, virtual object, robotic arm, etc. We will also compute the success rate achieved by the participant for a given task over a number of sessions. Impedance measurements will be collected during BMI testing sessions throughout the study. We will also document volunteered or observed adverse events at least weekly as part of the BMI training sessions as a measure of device safety. Subject may be asked at test sessions about level of fatigue, quality of sleep at home or other factors that may affect quality of testing performance.

At the end of each session, an investigator will remove the Patient Cable and clean the device. At a minimum, the Patient Pedestal should be cleaned every 7 days by a family member, caregiver, medical professional, or study team member. We will provide detailed cleaning instructions to the participant and anyone who may assist with the cleaning. We will monitor the subject's temperature on days that BMI testing occurs as this can be an early indicator of infection. In addition, we will instruct the subject to monitor and record their own temperature daily as well. A family member or caregiver will be asked to inspect the Patient Pedestal sites on a daily basis to identify any changes that may indicate an infection such as erythema, drainage, ecchymosis, pain, or unusual redness along the lead tunnel or pedestal. The study neurosurgeon and PI will train the research team and family member or caregiver in how to monitor wound healing.

Sleep Diary:

We may ask the participant to maintain a sleep diary which measures the amount and quality of sleep each night.

In-Home Sleep Evaluation:

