Individuals may experience frustration during BMI training sessions, particularly early in the study. For the extension study, participants will be informed that it is likely that signal quality will degrade over time. This may make it more difficult to complete the tasks so the difficulty and complexity may need to be reduced. Participants can be scheduled for appointments to speak with a psychologist throughout the study (approximately 1, 3, 6 and 9 months after implantation and again prior to explantation) to discuss any concerns they have during the study. The visits will occur every 3 months during the extension study as well. In addition, physician-investigators may refer the subjects to additional psychological appointments at their discretion.

Risks of EEG/EKG Recording (Extension Study)

Minor skin irritation may develop from the placement and removal of EKG and EEG electrodes.

Steps taken to minimize these risks:

Cleaning the skin after removal of the electrodes will reduce the risk of skin irritation. If skin irritation does occur, an over-the-counter ointment can remedy this.

Risks of In-Home Sleep Evaluation (Extension Study)

Participant may experience fatigue following sleep evaluation, if amount of sleep was insufficient or below normal amount.

Steps taken to minimize these risks:

Participant and caregiver will be asked to ensure that participant does not perform any activities that would invite risk of injury until the fatigue has subsided..

Risks of Pregnancy (Core Study and Extension Study)

Women who are, or plan to become, pregnant are excluded from the study due to potential risks to the unborn fetus or themselves. These risks include radiation exposure during x-ray or CT imaging which may lead to birth defects, mental impairment, cancer, or miscarriage. There are no known risks associated with undergoing an MRI scan while pregnant and the risks of MRI to the fetus are felt to be very small, but are nevertheless also not known. Any complications during surgery would put the fetus at risk for distress. We do not believe that pregnancy would carry any additional risks while the array is implanted, however this has not been studied and therefore the risks are unknown.

Steps taken to minimize these risks:

Study investigators will discuss the risks of pregnancy during the course of the study and will advise women against becoming pregnant. Women will be advised to notify the study team immediately if they learn they are pregnant.

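### The Aim 4 sleep regression adjusts for task difficulty but not for time since implant, so drift shared by sleep and performance could pass for a sleep association

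*Combined protocol and SAP*

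**What the plan says.** The Aim 4 analysis in section 3.5.3 reads "Sleep quality measures will be correlated to BMI performance on the following day while controlling for differences in task difficulty". A second sentence has linear regression identify the sleep metrics that predict best. No time term, participant term, significance level or test is given.

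Other parts of the document bear on this:

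- Section 1.3 says of the extension that "we may see a decline in BMI performance over time as signal quality declines". Section 4.1, on BMI training, tells participants that "it is likely that signal quality will degrade over time" and that task difficulty and complexity may have to come down as a result.
- In the same section 3.5.3, Aim 2 regresses success rate and computer-assist level over the duration of the trial, so performance is treated there as changing with time.
- Section 1.3 says sleep will be measured nightly for a set period but gives no length. The diary and in-home evaluation in section 3.4.2 are optional.
- Section 10.1 says the date and time of each session are saved with the data.

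**The concern.** Two series that both drift over the same window are correlated even when neither affects the other. The plan anticipates drift in performance. If a sleep measure also drifts, for example through ageing, health or season, a regression without time credits sleep with part of the performance change. Because the aim is to find the best predictors, the ranking of metrics could also favour whichever one happens to trend.

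At stake is whether a reported sleep association can be told apart from change since implant. Section 3.4.2 states the goal as how normal sleep affects neural activity and performance, so readers are likely to take the result as an effect.

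**Working it through.** The plan gives no sample size, effect size or error rate for Aim 4, so there is no figure to reproduce. The check asks how large the artefact could be.

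**Inputs.** From the documents: next-day performance as outcome, sleep measures as predictors, task difficulty as the only covariate. Assumed, because the documents give no values: one participant, 30 or 60 nights, no true link between sleep and performance, linear trends in both, and a two-sided 5% test on the sleep coefficient.

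**Step 1: induced correlation.** If time explains a share S of the sleep variance and P of the performance variance within the window, the spurious correlation is rho = sqrt(S x P). This gives sqrt(0.10 x 0.10) = 0.100, sqrt(0.10 x 0.25) = 0.158 and sqrt(0.25 x 0.25) = 0.250. If S = 0, rho = 0.

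**Step 2: credit for the difficulty term.** If difficulty correlates r with time, adjusting for it leaves a fraction 1 - r^2 of the time variance. A share S becomes S(1 - r^2) / [S(1 - r^2) + 1 - S]. With equal shares in both series, rho equals this reduced share.

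- r = 0.5, shares 25%: 0.1875 / 0.9375 = 0.200. Shares 10%: 0.075 / 0.975 = 0.077.
- r = 0.8, shares 25%: 0.09 / 0.84 = 0.107. Shares 10%: 0.036 / 0.936 = 0.038.

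**Step 3: rejection rates by simulation.**

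| Trend shares (sleep, performance) | Difficulty and time | rho | 30 nights | 60 nights |
|---|---|---|---|---|
| 10%, 10% | unrelated | 0.100 | 9% | 13% |
| 10%, 25% | unrelated | 0.158 | 14-15% | 24% |
| 25%, 25% | unrelated | 0.250 | 31% | 52-53% |
| 10%, 10% | r = 0.5 | 0.077 | 7% | 9% |
| 25%, 25% | r = 0.5 | 0.200 | 20% | 35% |
| 10%, 10% | r = 0.8 | 0.038 | 5% | 6% |
| 25%, 25% | r = 0.8 | 0.107 | 9-10% | 13% |
| no sleep trend | unrelated | 0 | 5% | 5% |

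**Hand check.** With d = atanh(rho) x sqrt(n - 4), the rejection rate is about P(Z > 1.96 - d) + P(Z < -1.96 - d). For rho = 0.25: at n = 30, d = 0.2554 x 5.099 = 1.302, giving 26%; at n = 60, d = 0.2554 x 7.483 = 1.911, giving 48%. For rho = 0.10 it gives 8% and 12%. A separate simulation with nights placed at random gave 25% and 48% for the 25% shares. Differences of a few points reflect the approximation and the placing of nights.

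**Step 4: does calendar length matter by itself?** For a slope of a SD per year over T years, the share is a^2 v / (1 + a^2 v), with v = T^2 / 12. At a = 0.5 and T = 4, a^2 v = 0.25 x 1.333 = 0.333 and the share is 0.333 / 1.333 = 25%. At a = 2 and T = 1, a^2 v = 4 x 0.0833 = 0.333, again 25%. Simulating the same shares within one year gave essentially the same rates. What counts is how far both series drift within the window.

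**Step 5: adding time.** With linear drift, a linear time term returned the rejection rate to about 5%.

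**The case against.** The strongest reply is that this is a conditional risk, not a demonstrated flaw. No section says that sleep trends, and if only one series drifts the rate stays at about 5%. That stands.

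Performance may not fall on balance either: section 1.3 wants to learn whether "neuroplasticity, or novel training methods, can compensate for this degradation in performance". The planned covariate may also carry part of the drift, since difficulty may be lowered as signals degrade. That stands too, which is why the table gives difficulty its credit. But the plan does not ensure that difficulty follows time closely.

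The plan states no test, so a false-positive rate measures a decision rule it does not contain. This is fair, and the rates are only a yardstick. The induced correlation in Step 1 needs no test and can still distort the ranking of metrics.

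A reader might infer something stronger: that sleep data will accrue almost weekly for years. Section 3.4.2 says "Subject may be asked at test sessions about level of fatigue, quality of sleep at home", "At least 1 session per week will be attempted while the array is implanted" and "we may not conduct testing sessions for up to 8 weeks per year", and section 3.3.3 lets participants "decide to extend the implantation for any duration between 6 months and 4 years". The documents do not support that reading. The question is optional, is listed among factors that may affect test performance, and is never named as Aim 4 data. Section 1.3 reads more like a bounded block of nights.

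**Conclusion.** The point holds in conditional form and is minor. The Aim 4 model omits time although the protocol anticipates decline and models time for Aim 2. If a sleep measure also drifts within the window, the result cannot be separated from change since implant. Under the assumed 10-25% shares, a nominal 5% test rejects about 9-31% of the time at 30 nights and 13-53% at 60 when difficulty is unrelated to time, and about 5-10% and 6-13% when difficulty correlates 0.8 with time. The true size is unknown, because trend sizes, number of nights and window length are all assumptions.

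A reader might also infer that only a window of several years is exposed and that a year or less is safe. The documents give no drift rate, and Step 4 shows that any such cut-off comes from the slope assumed. Nor do they support saying that the planned analysis will produce a false sleep effect. Aim 4 is exploratory and does not enter the success criterion or the safety assessment.

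**What to change.** In the Aim 4 paragraph of section 3.5.3, state that each sleep model is fitted within participant, that time since implant is added beside task difficulty, and that the sleep estimate is reported with and without the time term. If an association appears only without it, report it as not separable from change over time.

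This is a change of wording only. Session dates are already saved, no procedure is added, and within-participant fitting matches the single-subject approach stated for the core study in section 2.5.2.

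The cost is some power. For an assumed true correlation of 0.4, a linear time term changes power at 30 / 60 nights as follows:

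- no sleep trend: 61 to 59% / 90 to 89%;
- 10% sleep trend: 61 to 55% / 89 to 86%;
- 25% sleep trend: 63 to 48% / 90 to 80%.

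If slow change in sleep really drives performance, the time term removes that information, which is why both estimates should be shown. A linear term does not remove non-linear or seasonal drift. With an annual cycle explaining 25% of both series over an assumed four-year span, it leaves rejection at about 25% / 48%. It also does nothing about night-to-night autocorrelation. The write-up should state these limits.
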